11.1.2 Serious Adverse Event (SAE)

A SAE is an adverse event that:

- Results in death. **NOTE:** Death due to disease progression should not be reported as a SAE, unless it is attributable by the site investigator to the study drug(s)
- Is life-threatening (defined as an event in which the subject was at risk of death at the time of the event; it does not refer to an event which hypothetically might have caused death if it were more severe)
- Requires inpatient hospitalization for >24 hours or prolongation of existing hospitalization. **NOTE:** Hospitalization for anticipated or protocol specified procedures such as administration of chemotherapy, central line insertion, metastasis interventional therapy, resection of primary tumor, or elective surgery, will not be considered serious adverse events.
- Results in persistent or significant disability/incapacity
- Is a congenital anomaly or birth defect
- Is an important medical event (defined as a medical event(s) that may not be immediately life-threatening or result in death or hospitalization but, based upon appropriate medical and scientific judgment, may jeopardize the subject or may require intervention (e.g.,

medical, surgical) to prevent one of the other serious outcomes listed in the definition above). Examples of such events include, but are not limited to, intensive treatment in an emergency room or at home for allergic bronchospasm; blood dyscrasias or convulsions not resulting in hospitalization; or the development of drug dependency or drug abuse.

11.1.3 Unexpected Adverse Event

For this study, an AE is considered unexpected when it varies in nature, intensity or frequency from information provided in the current IB, prescribing information or when it is not included in the informed consent document as a potential risk. Unexpected also refers to AEs that are mentioned in the IB as occurring with a class of drugs or are anticipated from the pharmacological properties of the drug, but are not specifically mentioned as occurring with the particular drug under investigation.

11.1.4 Relatedness

AEs will be categorized according to the likelihood that they are related to the study drug(s). Specifically, they will be categorized using the following terms:

Unrelated	Adverse Event is not related to the study drug(s)
Unlikely	Adverse Event is doubtfully related to the study drug(s)
Possible	Adverse Event may be related to the study drug(s)
Probable	Adverse Event is likely related to the study drug(s)
Definite	Adverse Event is clearly related to the study drug(s)

11.1.5 Pregnancy

If, following initiation of the study drugs, it is subsequently discovered that a subject is pregnant or may have been pregnant at the time of study drug exposure, including during at least 6 half lives after study drug administration, the study drug will be permanently discontinued in an appropriate manner (eg, dose tapering if necessary for subject safety).

The site investigator must immediately notify HCRN who will then notify Worldwide Safety @BMS of this event via the HCRN Pregnancy Form in accordance with SAE reporting procedures. Follow-up information regarding the course of the pregnancy, including perinatal and neonatal outcome and, where applicable, offspring information must be reported on the HCRN Pregnancy Form. Any pregnancy that occurs in a female partner of a male study participant should be reported to HCRN who will then report it to BMS. Information on this pregnancy will be collected on the HCRN Pregnancy Form.

11.1.6 Overdose

An overdose is defined as the accidental or intentional administration of any dose of a product that is considered both excessive and medically important. All occurrences of overdose must be reported as a SAE.

11.2 Reporting

11.2.1 Adverse Events

- AEs will be recorded from time of signed informed consent until 100 days after discontinuation of study drug(s) or until a new anti-cancer treatment starts, whichever occurs first.
- AEs will be recorded regardless of whether or not they are considered related to the study drug(s).
- All AEs will be recorded in the subject's medical record and on the appropriate study specific eCRF form within the EDC system.
- AEs considered related to study drug(s) will be followed until resolution to Grade ≤ 1 or baseline, deemed clinically insignificant, and/or until a new anti-cancer treatment starts, whichever occurs first.

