1.3.2.1 Clinical Pharmacokinetics

The pharmacokinetics (PK) of nivolumab was studied in subjects over a dose range of 0.1 to 10 mg/kg administered as a single dose or as multiple doses of nivolumab every 2 or 3 weeks. The geometric mean (% CV%) clearance (CL) was 9.5 mL/h (49.7%), geometric mean volume of distribution at steady state (V_{ss}) was 8.0 L (30.4%), and geometric mean elimination half-life (t_{1/2}) was 26.7 days (101%). Steady-state concentrations of nivolumab were reached by 12 weeks when administered at 3 mg/kg Q2W, and systemic accumulation was approximately 3-fold. The exposure to nivolumab increased dose proportionally over the dose range of 0.1 to 10 mg/kg administered every 2 weeks. The clearance of nivolumab increased with increasing body weight. A PK analysis suggested that the following factors had no clinically important effect on the CL of nivolumab: age (29 to 87 years), gender, race, baseline LDH, PD-L1. A PK analysis suggested no difference in CL of nivolumab based on age, gender, race, tumor type, baseline tumor size, and hepatic impairment. Although ECOG status, baseline glomerular filtration rate (GFR), albumin, body weight, and mild hepatic impairment had an effect on nivolumab CL, the effect was not clinically meaningful. When nivolumab is administered in combination with ipilimumab, the CL of nivolumab was increased by 24%, whereas there was no effect on the clearance of ipilimumab. Additionally, PK and exposure response analyses have been performed to support use of 240 mg Q2W dosing as a substitute for the previously studied 3 mg/kg Q2W regimen. Using a PK model, exposure of nivolumab at 240 mg flat dose was identical to a dose of 3 mg/kg for subjects weighing 80 kg, which was the approximate median body weight in nivolumab clinical trials. The 240 mg q 2 week flat dose of nivolumab monotherapy has recently received FDA approval.

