10. Patients on Part B should be contacted weekly during Cycles 1 and 2. If a patient reports symptoms at any time during these cycles or abnormal labs are noted at the regularly scheduled visits (C1 D22, C2 D1 or D22) then more frequent laboratory testing and clinic visits are encouraged.. This decision is at the discretion of the site investigator.
11. An End of Treatment (EOT) visit should occur 30 and 100 days (\pm 7 days) from last dose of study drug. For patients experiencing toxicities, additional visits may be necessary and may occur every 2 weeks (\pm 3 days) until toxicities resolve, are stable, or start of new systemic therapy. Depending upon the toxicity, the every 2-week assessment may be accomplished via phone call, email or other avenues as appropriate. Mode of assessment will be at site investigator's discretion. If patients have progressive disease as the reason for discontinuation from study, the D100 may be a phone call.
12. Follow up is for subjects that have discontinued study treatment. Subjects should be followed every 3 months if < 3 years from study registration and every 6 months if 3-5 years from study registration. Patients who develop disease progression on Part B or on Part A (if ineligible for Part B) will be followed for survival only. Follow up may be accomplished via clinic visit, phone call, or other avenues as appropriate. A window of \pm 14 days will be applied to follow up.

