10.1.6 Adverse Events

Please see the current Investigator's Brochure for complete details regarding AEs of nivolumab. The most common side effects of nivolumab are:

- Fatigue
- Skin reactions: including rash, itching, hives, redness, and dry skin. Toxic epidermal necrolysis, a potentially life threatening disease characterized by blistering and peeling of the top layer of skin resembling that of a severe burn, has occurred in one subject who received ipilimumab after nivolumab treatment.
- Diarrhea
- Nausea
- Abdominal pain
- Decreased appetite
- Low red blood cells
- Fever
- Joint pain or stiffness

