11.2.2 Serious Adverse Events (SAEs)

11.2.2.1 Site Requirements for Reporting SAEs to HCRN

- SAEs will be reported from time of signed informed consent until 100 days after discontinuation of study drug(s) or until a new anti-cancer treatment starts, whichever occurs first.
- SAEs will be reported on the SAE Submission Form **within 1 business day** of discovery of the event.
- SAEs include events related and unrelated to the study drug(s).
- All SAEs will be recorded in the subject's medical record and on the appropriate study specific eCRF form within EDC system.
- All SAEs regardless of relation to study drug will be followed until resolution to \leq Grade 1 or baseline and/or deemed clinically insignificant and/or until a new anti-cancer treatment starts, whichever occurs first.

The site will submit the completed SAE Submission Form to HCRN **within 1 business day** of discovery of the event. The form may be submitted to HCRN electronically to [contact]. The site investigator is responsible for informing the IRB and/or other local regulatory bodies as per local requirements. The original copy of the SAE Submission Form and the email correspondence must be kept within the study file at the study site.

Once the SAE has resolved (see resolution guidelines listed in 11.2.2.1), sites must submit a follow-up SAE Submission Form within a reasonable timeframe to HCRN electronically to [contact].

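### AE and SAE recording stops at the first new anti-cancer treatment, even for drug-related events, so the post-treatment safety window depends on outcome

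*Combined protocol and SAP*

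**What the plan says.** Section 11.2.1 starts AE recording at consent and runs it "until 100 days after discontinuation of study drug(s) or until a new anti-cancer treatment starts, whichever occurs first". Events attributed to study drug are followed until they return to Grade 1 or baseline, are "deemed clinically insignificant, and/or until a new anti-cancer treatment starts, whichever occurs first".

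Section 11.2.2.1 repeats the window for serious events: "SAEs will be reported from time of signed informed consent until 100 days after discontinuation of study drug(s) or until a new anti-cancer treatment starts". SAE follow-up covers every SAE, related or not, and has the same end-point: "deemed clinically insignificant and/or until a new anti-cancer treatment starts, whichever occurs first".

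Footnote 11 of the study calendar (section 7) places end-of-treatment contacts at 30 and 100 days after the last dose. It keeps the later one for patients who stop because of progression: "If patients have progressive disease as the reason for discontinuation from study, the D100 may be a phone call". The additional two-weekly visits for unresolved toxicity end when new systemic therapy begins. Under footnote 12, patients who progress on Part B, or on Part A without being eligible for Part B, are then followed for survival alone.

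Toxicity of nivolumab monotherapy is a secondary objective (section 2.1.2) and a secondary endpoint (sections 2.2.2 and 12.7.2). Section 12.9 gives Part B its own safety analysis.

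**The concern.** Ending the collection of unrelated events when another regimen starts is reasonable. Here the same limit applies to events that the investigator attributes to study drug. As written, a site has no duty to report an immune-related SAE that begins the day after a switch, and it may stop following a related SAE that is still unresolved.

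The limit is not neutral with respect to outcome. The usual reason to start another anti-cancer treatment within 100 days is that the study treatment failed. Patients who progress and are re-treated quickly are therefore watched for less time than patients who stop for other reasons. If late immune-related events occur in that group, the toxicity summary will tend to understate them. The gap also passes downstream, because the adverse event summary for the data safety monitoring committee (section 13.2), reports to the drug supplier (section 11.2.2.2) and FDA reports (section 11.4) all draw on what sites submit.

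**Working it through.** The plan gives no figure for this point, so there is nothing to reproduce. The check is a comparison of the text, followed by arithmetic for scale only.

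**1. Is there an exception anywhere?**
- Sections 11.2.1 and 11.2.2.1: the cut-off applies to recording and follow-up, with no carve-out for related or immune-related events.
- Footnote 11: the day-100 contact is kept after progression, and nothing excuses patients already on another therapy. The extra toxicity visits stop at the switch.
- Synopsis, study design: AEs are to be captured continuously, but no end date is set, so this does not override section 11.2.
- Section 11.1.5, for contrast: pregnancy reporting reaches at least six half-lives after dosing, with no new-therapy limit. At 26.7 days that is 6 × 26.7 = 160.2 days. The protocol thus treats late exposure as relevant elsewhere.

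No exception was found.

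**2. Length of the window.** Let T be the day, counted from the last dose, on which new therapy starts. The window is W = min(100, T), and the days lost are 100 − T when T < 100. The documents do not give T, so the values below are assumed.

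**3. Drug still present at the switch.** Fraction remaining = 0.5^(T / half-life), using 26.7 days for nivolumab (section 1.3.2.1) and 14.7 days for ipilimumab (section 10.2.1).

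| T (assumed) | Window | Days lost | Nivolumab left | Ipilimumab left |
|---|---|---|---|---|
| 14 | 14 | 86 | 69.5% | 51.7% |
| 30 | 30 | 70 | 45.9% | 24.3% |
| 60 | 60 | 40 | 21.1% | 5.9% |
| 90 | 90 | 10 | 9.7% | 1.4% |

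The ipilimumab column counts from the last ipilimumab dose, so it fits only patients who stop during the combination phase. The nivolumab half-life is itself uncertain. Section 1.3.2.1 gives a coefficient of variation of 101%, and section 1.4 reports 12 to 20 days in the first-in-human study. At T = 30 that range leaves 0.5^(30/12) = 18% to 0.5^(30/20) = 35%. These figures describe exposure, not event risk.

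**4. Who is affected?** Only patients who start non-protocol treatment before day 100. Those who progress without re-treatment are recorded for the full 100 days. Patients who enter Part B receive study drug again, and their post-treatment window runs from the end of Part B. Section 11.2 does not define a new anti-cancer treatment, but section 12.9 plans a separate Part B safety analysis, so Part B cannot sensibly count as one.

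**5. After the change.** For related events W = 100 for every patient, whatever T is. For T = 14, 30, 60 and 90, this restores 86, 70, 40 and 10 days.

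**The case against.** The strongest reply is that this is a deliberate and consistent rule. Sections 11.2.1 and 11.2.2.1 and footnote 11 all stop at the next therapy, because attribution is confounded once another agent is given. The trial is non-randomised and its safety analysis is descriptive, so the unequal window biases no treatment comparison and touches neither the primary endpoint nor any decision rule. Most toxicity data come from the on-treatment period, which is unaffected. The rule also removes a duty to report; it does not forbid reporting. All of this stands and keeps the point modest. It does not explain why events judged related should fall under the same limit as unrelated ones.

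A reader might infer several stronger claims that the documents do not support:
- **That the protocol's own case history proves the gap.** Section 10.1.6 says that toxic epidermal necrolysis "has occurred in one subject who received ipilimumab after nivolumab treatment". In this trial that sequence is Part B, where the event would be recorded.
- **That a fixed share of late events is lost.** Assuming risk proportional to drug level, a half-life of 26.7 days and a switch at day 28, one obtains 44%; half-lives of 12 to 20 days give 20% to 36%. But sections 1.3.2.3 and 1.4 report no evident relation between nivolumab dose and toxicity, so the assumption lacks support.
- **That some 30 to 35 clear cell patients are affected.** This comes from 134 × (1 − 0.28) − 67 = 29.5, and 134 × (1 − 0.241) − 67 = 34.7. Here 28% is the planned 1-year PFS, 24.1% is the weighted mean over the four PD-L1 groups (0.45 × 13% + 0.25 × 19% + 0.15 × 35% + 0.15 × 55%), and 67 is half of 134. The result includes deaths and patients who start nothing new within 100 days. It is not a count of patients with a shortened window.
- **That every SAE should be collected after a switch.** Each one needs a site form within one business day, forwarding to the supplier within one business day of receipt, and sponsor-investigator review (sections 11.2.2 and 11.3). For unrelated events on another regimen, that burden is debatable.

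**Conclusion.** The point holds in a limited form. As written, section 11.2 closes AE and SAE recording, and follow-up of related AEs and of all SAEs, on the day non-protocol anti-cancer therapy starts, with no exception for drug-related events. For patients who switch before day 100 the safety window is min(100 days, time to next therapy). It is shortened by outcome, so late immune-related toxicity may be undercounted in that group.

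The text alone establishes this, without any pharmacokinetic assumption. Its size in this trial cannot be stated: the proportion of patients who switch within 100 days could be anything from 0% to 100% on the documents, and the share of events lost is unknown. It would be wrong to conclude that late toxicity goes unrecorded in all patients who progress, because those who enter Part B, or who start nothing new before day 100, are not affected. This is an inexpensive improvement to safety capture and does not threaten the efficacy conclusions.

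**What to change.** In sections 11.2.1 and 11.2.2.1:
- Record AEs and SAEs judged possibly, probably or definitely related to study drug (the categories of section 11.1.4) until day 100 after the last dose, regardless of new therapy.
- Follow related SAEs to resolution or stabilisation, regardless of new therapy.
- Keep the new-therapy cut-off for events judged unrelated or unlikely.
- Tabulate events with onset after new therapy on a separate line.

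The day-100 contact in footnote 11 already gives an occasion to collect these data, by phone where progression was the reason for stopping. Treatment and sample size do not change. The costs are less certain attribution once another agent has been given, which the separate line makes visible, and a modest number of additional reports on the existing one-business-day timelines. Restricting the extension to related events keeps that number down.

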11.2.2 Serious Adverse Events (SAEs)

11.2.2.1 Site Requirements for Reporting SAEs to HCRN

- SAEs will be reported from time of signed informed consent until 100 days after discontinuation of study drug(s) or until a new anti-cancer treatment starts, whichever occurs first.
- SAEs will be reported on the SAE Submission Form **within 1 business day** of discovery of the event.
- SAEs include events related and unrelated to the study drug(s).
- All SAEs will be recorded in the subject's medical record and on the appropriate study specific eCRF form within EDC system.
- All SAEs regardless of relation to study drug will be followed until resolution to \leq Grade 1 or baseline and/or deemed clinically insignificant and/or until a new anti-cancer treatment starts, whichever occurs first.

The site will submit the completed SAE Submission Form to HCRN **within 1 business day** of discovery of the event. The form may be submitted to HCRN electronically to [contact]. The site investigator is responsible for informing the IRB and/or other local regulatory bodies as per local requirements. The original copy of the SAE Submission Form and the email correspondence must be kept within the study file at the study site.

Once the SAE has resolved (see resolution guidelines listed in 11.2.2.1), sites must submit a follow-up SAE Submission Form within a reasonable timeframe to HCRN electronically to [contact].

11.2.2.2 HCRN Requirements for Reporting SAEs to BMS

HCRN will report all SAEs to BMS **within 1 business day** of receipt of the SAE Submission Form from a site. Follow-up information will be provided to BMS as it is received from site. Contact information for sending SAE information to BMS below:

SAE Email Address: [contact]

SAE [contact]

HCRN and the Sponsor-investigator will ensure that all SAEs in the clinical database are reported to BMS and any applicable health authority during the conduct of the study. This reconciliation will **occur at least quarterly** and be initiated by HCRN on behalf of the sponsor-investigator. HCRN will request on behalf of the sponsor-investigator a reconciliation report from: [contact]. During reconciliation, any events found to not be reported previously to BMS must be sent to [contact].

11.3 Sponsor-Investigator Responsibilities

HCRN will send a SAE summary to the sponsor-investigator **within 1 business day** of receipt of SAE Submission Form from a site. The sponsor-investigator will promptly review the SAE summary and assess for expectedness and relatedness.

11.4 HCRN Responsibilities to FDA

HCRN will manage the Investigational New Drug Application (IND) associated with this protocol on behalf of the sponsor-investigator. HCRN will cross-reference this submission to the BMS's parent IND at the time of submission. Additionally, HCRN will submit a copy of these documents to BMS at the time of submission to FDA.

HCRN will be responsible for all communication with the FDA in accordance with 21CFR312 including but not limited to the 7 and 15 Day Reports, as well as an Annual Progress Report. Additionally, HCRN will submit a copy of these reports to BMS at the time of submission to FDA.

11.5 IND Safety Reports Unrelated to this Trial

BMS will provide to HCRN IND safety reports from external studies that involve the study drug(s) per their guidelines. HCRN will forward safety reports to the sponsor-investigator who will review these reports and determine if revisions are needed to the protocol or consent. HCRN will forward these reports to participating sites **within 1 business day** of receiving the sponsor-investigator's review. Based on the sponsor-investigator's review, applicable changes will be made to the protocol and informed consent document (if required). All IND safety reports will also be made available to sites via the EDC system.

Upon receipt from HCRN, site investigators (or designees) are responsible for submitting these safety reports to their respective IRBs, as per their IRB policies.

12. STATISTICAL METHODS

12.1 Part A Primary Endpoint

The primary focus of this trial will be in the evaluation of PD-L1 to predict outcome and, also, secondarily to use the PRP model as a basis for outcome prediction. We expect that about 45% (or 54 expected) patients will have 0% PD-L1 and roughly 15% (or 18 expected) patients will express PD-L1 > 20%, which, given the sample size of 120 ccRCC patients provides 90% power using a 0.05 level two-sided test to test the hypothesis that PD-L1 > 20% will be associated with significantly improved 1-year PFS rate for patients treated with PD-1 blockade (55% vs 13% taken as a binomial quantity). Considering the four groups of PD-L1 expression (0%, 1-5%, 5-20%, >20%), and with an expected patient allocation within groups of (45%, 25%, 15%, 15%),

the Cochran-Armitage test gives at least 90% power to detect a trend in 1-year PFS of (13%, 19%, 35%, 55%) using a two-sided 0.05 level test for trend. Modest changes in the proportions of patients in the various PD-L1 categories will not substantially affect the power. For example, if the distribution across PD-L1 categories is [25%, 25%, 25%, 25%] rather than the anticipated [45%, 25%, 15%, 15%] the power for the trend test remains greater than 90%.

As a secondary objective, we will apply the PRP model, developed in the DF/HCC Kidney SPORE Project 4, to assign each patient a probability of having PFS >1 year. The validity of the model will be assessed by the Brier score as well as via evaluation of the AUC. The exact distribution is unknown, but assuming an overall 1-year PFS of 28% and that 40% of patients are expected to be “positive” by the PRP model, 120 ccRCC patients give 90% power to detect a 29% higher 1-year PFS between 48 positive patients and 72 negative patients (via Fisher’s exact test and assuming a difference in PFS of 46% vs 17%). All testing above will be done at 1-sided $\alpha=0.025$. The specific distributional breakdowns are unknown but the power is relatively robust. For example, if the split between positive and negative is more even (50/50) then power for the above difference in 1-yr PFS remains over 90%. If the actual difference in 1-yr PFS is smaller than anticipated for example 25% (44% vs 19%) then the test will still have at least 80% power.

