The OS benefit, history of durable responses and tolerability of nivolumab suggest that it be a preferred treatment for a subset of treatment naïve patients. However, currently there is very limited single agent data on the activity of nivolumab in treatment naïve patients with ccRCC. The BMS-sponsored study CA 209009 included 23 subjects with treatment-naïve RCC. In these patients, treatment with nivolumab 10 mg/kg every 3 weeks resulted in an overall response rate of 13% (3/23).

Further anti-PD1/PDL1 therapies have shown anti-tumor activity in patients with over 20 different types of malignancy; however only anecdotal reports exist for this treatment approach in patients with non-clear cell (ncc)RCC.

Finally, the combination of nivolumab and the CTLA4 checkpoint inhibitor ipilimumab has produced greater antitumor activity than nivolumab alone in patients with advanced melanoma and encouraging response rates in patients with ccRCC. It remains uncertain whether the addition of ipilimumab to nivolumab in patients who have failed to respond to nivolumab monotherapy could produce antitumor activity. To address all these concerns, we propose to conduct a study of nivolumab monotherapy in treatment naïve patients with advanced cc or nccRCC (Part A), with the addition of ipilimumab in patients with disease progression or who have failed to respond by 48 weeks into therapy (Part B) that will focus on uncovering biomarkers of response and resistance to PD-1 blockade, as well as possible predictors of subsequent response to CTLA-4 blockade.

In this trial, we examine the following questions:

- 1) How active is PD-1 blockade in treatment naïve kidney cancer?
- 2) What factors, in addition to PD-L1 expression, can reliably predict durable response?
- 3) Do gene expression signatures which are likely capturing the presence, magnitude, and activity of adaptive immune infiltrates reliably predict durable response?
- 4) Is there a threshold for PD-L1 expression in either the tumor or immune cell infiltrate that accurately predicts durable response?
- 5) Is PD-L1 expression uniform and stable in an individual tumor and between a primary tumor and its metastases?
- 6) What are the mechanisms of innate resistance to PD-1 pathway blockade?

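### The planned PRP analysis can show that PRP is associated with 1-year PFS, but not that it adds anything to PD-L1

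*Combined protocol and SAP*

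**What the plan says.** Section 12.1 (Part A Primary Endpoint) and the synopsis (Statistical Considerations) make PD-L1 the primary predictor of 1-year PFS and PRP the secondary one. For PRP, the sample size statement is that "120 ccRCC patients give 90% power to detect a 29% higher 1-year PFS between 48 positive patients and 72 negative patients", using a one-sided Fisher exact test at 0.025 with 46% against 17%, and "assuming an overall 1-year PFS of 28% and that 40% of patients are expected to be “positive” by the PRP model". Model performance is covered in one sentence: "The validity of the model will be assessed by the Brier score as well as via evaluation of the AUC". No comparator is named for either measure.

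For PD-L1, the same section plans four expression groups holding 45%, 25%, 15% and 15% of patients, with 1-year PFS of 13%, 19%, 35% and 55%.

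The study questions in the synopsis and in Section 1.7 include: "What factors, in addition to PD-L1 expression, can reliably predict durable response". Section 1.6 calls for prospective validation of gene signatures and other factors, both alone and combined with PD-L1. Section 2.1.2 words the PRP objective more narrowly, as the 1-year PFS rate according to the PRP model, by RECIST and irRECIST. Section 2.1.3 lists novel predictive biomarkers as exploratory and gives no method. Nowhere is there a test of PRP adjusted for or stratified by PD-L1, a joint model, or a comparison of the AUC or Brier score of PRP with that of PD-L1.

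**The concern.** PD-L1 and PRP are assessed in the same ccRCC patients, and the plan assumes that PD-L1 alone moves 1-year PFS from 13% to 55%. If PRP overlaps with PD-L1, some or all of the difference between PRP-positive and PRP-negative patients may be PD-L1 seen through another score. Overlap is plausible on the protocol's own account: Section 1.7 describes PD-L1 expression as an adaptive response to interferon-gamma, and Section 8.1.2 plans an interferon-gamma signature and links PD-L1 to Fuhrman grade. The components of PRP are not given, so the degree of overlap is unknown.

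What is at stake is the reading of the first-listed secondary objective. A significant Fisher test with a respectable AUC could be reported as support for a better biomarker, when the planned analyses cannot tell added information from repeated information. A Brier score without a reference has the same weakness: giving every patient the assumed overall rate of 28% already scores 0.28 × 0.72 = 0.20.

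**Working it through.** **Inputs, all from Section 12.1.** PD-L1 group shares w = (0.45, 0.25, 0.15, 0.15); 1-year PFS p = (0.13, 0.19, 0.35, 0.55); 48 PRP-positive and 72 PRP-negative patients; Fisher exact test, one-sided 0.025.

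**Step 1: the plan's own figure.** Exact enumeration over two binomials with 46% vs 17% and 48 vs 72 patients gives 90.3% power (stated: 90%). It reproduces.

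**Step 2: the ceiling.** Let PRP-positive be exactly the top 40% by PD-L1: everyone above 20%, everyone in 5-20%, and 10 of the 25 percentage points in 1-5%. PRP then carries no information beyond PD-L1.
- PRP-positive: (0.15×55 + 0.15×35 + 0.10×19)/0.40 = 15.4/0.40 = 38.5%
- PRP-negative: (0.45×13 + 0.15×19)/0.60 = 8.7/0.60 = 14.5%

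The difference is 24 points, against the 29 planned for PRP. The planned test is significant 80.2% of the time.

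**Step 3: weaker overlap, still no added value.** Overlap is modelled as a correlation between normal scores underlying PD-L1 and PRP. The correlations are assumptions.

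| Correlation | PFS, PRP+ vs PRP- | Fisher test significant |
|---|---|---|
| 1.0 | 38.5% vs 14.5% | 80% |
| 0.9 | 37% vs 15.5% | 69-70% |
| 0.7 | 33.5% vs 17.8% | 41-43% |
| 0.5 | 30.6% vs 19.8% | about 21% |
| 0.3 | 27.8% vs 21.6% | 8.5% |
| 0 | 24.1% vs 24.1% | 1.6% |

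Where a range is shown, the upper value fixes the groups at 48 and 72 and the lower lets their sizes vary.

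**Step 4: a weaker PD-L1 effect.** Keep complete overlap but shrink each PD-L1 rate toward the implied mean of 24.1% (0.45×13 + 0.25×19 + 0.15×35 + 0.15×55), that is 24.1 + s(p - 24.1). The test is significant 80%, 54%, 26% and 8% of the time for s = 1, 0.75, 0.5 and 0.25. In the other direction, shifting the PD-L1 rates to average the 28% assumed for PRP raises the ceiling to 83.0%.

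**Step 5: an adjusted test.** A one-sided 0.025 Cochran-Mantel-Haenszel test stratified by the four PD-L1 groups (N = 120, 40,000 simulated trials) rejects 2.6-2.9% of the time when PRP adds nothing, at every degree of overlap tried. For its power, assume a within-group odds ratio of (0.46/0.54)/(0.17/0.83) = 4.16, and let a share λ of PRP status follow the PD-L1 ranking, the rest being random. Power is about 84% at λ = 0, 80% at 0.5, 61% at 0.8 and 32% at 1. At λ = 1 only the 1-5% group (0.25 × 120 = 30 patients) contains both PRP categories, so only those patients inform the test.

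**Step 6: discrimination on the plan's figures.** The four PD-L1 groups imply an AUC of 0.70. PRP as a dichotomy that meets its target exactly has sensitivity 0.40×0.46/0.286 = 0.643 and specificity 0.60×0.83/0.714 = 0.697, so AUC = (0.643 + 0.697)/2 = 0.67. PRP could meet its design target and discriminate no better than PD-L1, and no planned analysis would show it. A continuous PRP score might do better; the documents do not say.

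**The case against.** The strongest defence is that the Fisher test answers the objective as written. Section 2.1.2 asks for 1-year PFS by PRP, and neither it nor Section 12.1 promises that this test will show PRP adding to PD-L1. That stands. The null of the test is no association between PRP and PFS, and under that null it rejects 1.6% of the time. A reader might infer from the 80% figure that the type I error is inflated. It is not, because in that scenario PRP really is associated with PFS, through PD-L1.

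A reader might also infer that the test would be significant about 80% of the time whenever PRP adds nothing, or that any score correlated with PD-L1 would pass. The documents support neither. The 80% is a ceiling that needs complete overlap and the full planned gradient. The overlap is not given, and Section 1.6 itself reports doubtful predictive value of tumor PD-L1 in RCC, partly on overall survival.

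Nor is the question about other predictors abandoned. Its wording can be read as predictors other than PD-L1, Sections 2.1.3 and 8.1.2 plan exploratory work on such predictors, and the data would allow an adjusted analysis later. What remains is that no such analysis is specified, and one chosen after the results are known is weaker evidence.

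A last objection concerns the remedy: comparing the apparent AUC of fitted models favours the larger model. In simulation (N = 120, about 29 patients progression-free at 1 year, PRP adding nothing), apparent AUC rose in 83-88% of trials, by about 0.015 on average. That is correct and is built into the fix.

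**Conclusion.** The concern holds as a gap in what the PRP analysis can support, not as an error in the test. A significant PRP result would show association with 1-year PFS and leave open whether PRP adds to PD-L1. If it adds nothing, significance would occur between about 2% and about 80% of the time, depending on an overlap that the documents do not give. This range assumes the plan's PD-L1 shares and rates, a 40% PRP-positive fraction and 120 patients. The omission itself is certain; the size within the range is not. The change is worth making because the protocol raises the question of value beyond PD-L1 and the needed data are already to be collected.

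**What to change.** In Section 12.1 and the synopsis:

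1. Keep the Fisher test and state that it, with the stand-alone AUC and Brier score, shows association and overall performance only.
2. Pre-specify one PD-L1-adjusted test of PRP at one-sided 0.025: either a logistic model of 1-year PFS on PD-L1 group plus PRP, or a Cochran-Mantel-Haenszel test stratified by PD-L1 group. Reserve any claim of value beyond PD-L1 for it.
3. Report AUC and Brier score for PD-L1 alone and for PD-L1 plus PRP. Give the change with bootstrap or cross-validated optimism correction and an interval, for both RECIST and irRECIST.
4. State the power of the adjusted test over a range of overlaps, and that a non-significant adjusted result is inconclusive.

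The cost is SAP wording and one further model, with no new patients, samples or visits. The drawback is power: about 32-84% for an assumed within-group odds ratio near 4, lowest where PRP and PD-L1 overlap most.
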